## **15.0 Risks to Subjects\***

15.1 There is a minimal risk for injury. Minimal risks that may occur related to study participation include muscle soreness during or after exercise, discomfort in joints of lower and upper extremity during or after exercise, which both are expected to occur infrequently.

15.2 N/A

15.3 N/A

15.4 N/A

## **16.0 Potential Benefits to Subjects\***

16.1 Potential benefits that individual participants may experience from taking part in the research include decrease in pain and disability.

16.2 N/A.

## **17.0 Data Management\* and Confidentiality**

17.1 For this study, the endpoint is defined as based on previous research regarding home exercise and disability with low back pain we determine that 40 participants (20 in each group) will be necessary, alpha set *a priori* to .05. 40 participants include a 15% attrition rate. Descriptive statistics will be used for age, height, mass. Mean differences, confidence intervals and effect sizes will be used to analyze questionnaires. An activation ratio will be used for the lateral abdominal wall measurements. The static positioning measuring will be used as the numerator and the exercise starting position will be used at the denominator to calculate a ratio.

17.2 All computers storing electronic data will be password protected and only study team members will have access to the passwords. Computers will always remain behind locked doors when not supervised by study team members. All external hard drives used to back up storage will be password protected. Only study team members will have access to these passwords. These passwords will be changed frequently and will be changed immediately if compromised at any point in time.

Participant numbers will be generated by using the IRB # and will be assigned a number (i.e. IRB#12345\_001) as they are enrolled in the study. This number will be utilized in place of any other identifier for the remainder of the study.

Identifiers with de-identified coding will be stored electronically on Redcap and will be deleted after a minimum of 5 years from the time the study closes.

17.3 To ensure quality control of collected data, the 7 exercises performed by participants at their home setting will be demonstrated and taught during the first exercise session with the researcher. Weekly video calls through zoom and emails will be conducted to answer any comments or concerns regarding the exercise completion. We will get in touch with the participants weekly either using zoom (video call) or by email to answer any comments or concerns regarding the exercise completion. The participants email will be provided to the principal investigator when they email showing interest in the study. The leaderboard group will have on demand video that can be accessed at any time and the control take-home packet group will have a packet with pictures and descriptions of the exercises.

17.4 Questionnaire data will be collected electronically through REDCap. All data will be de-identified at all stages of collection and analysis. Data will be stored until study closure, then will be maintained on password protected lab computer and de-identified for at least 5 years. Signed electronic consent forms will be stored for a minimum of 5 years before being destroyed as well. All questionnaires and surveys will be kept in de-identified electronic folders on REDCap, separate from electronically signed consent forms, also for a minimum of 5 years before being destroyed. Only the PI and study team will have access to the data. Ultrasound measurements of the lateral abdominal wall will be de-identified and stored on password protected laboratory computer.

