## Study Summary

Study Title	The Effects of a Gamified Rehabilitation Protocol Compared to an At-Home Exercise Packet in Individuals with Low Back Pain
Study Design	Randomized Controlled Trial
Primary Objective	To measure the change in pain and disability before, during and after a competitive home exercise program compared to a take home packet exercise program.
Secondary Objective(s)	
To quantify adherence and compliance of individuals completing a competitive, gamified home exercise program compared to a traditional autonomous exercise program.
 
To measure the change of Ultrasound thickness and onset of muscle activation of the lateral abdominal wall in individuals with non-specific low back pain during static and exercise positioning following a 6-week home exercise program

Research Intervention(s)/Investigational Agent(s)	None
IND/IDE #	N/A
Study Population	
Individuals aged 18-45 with non-specific low back pain
 
Inclusion Criteria: ages 18-45, biological sex of Male or Female, self-reported low back pain within the previous 6 months or greater than 3 episodes within the past 3 years
 
Exclusion Criteria: Currently seeing and or receiving care from an athletic trainer, physical therapist, or other rehabilitation specialist in the previous 6 months, low back pain conditions such as lumbar spondylosis, herniated disc, spondylolisthesis, previous spine surgery, currently pregnant, experiencing neurological symptoms or other muscular abnormalities.
 
Unable to assume the exercise starting position.
 
Current use of lidocaine patches or prescription pain medicine.

Sample Size	40
Study Duration for individual participants	6-week intervention + 12, 18, 24-month follow-ups
Study Specific Abbreviations/ Definitions	NSLBP: non-specific low back pain; ODI: Oswestry Disability Index; NPRS; Numeric Pain Rating Scale; SUS: System Usability Scale; EARS: Exercise Adherence Rating Scale; CES: Credibility and Expectancy; PCS: pain catastrophizing scale; PBP: Prone Bridge Plank; GROC; Global Rating of Change Scale; TESP: Torso Elevated Side Plank; FESP: Foot Elevated Side Plank; TrA: Transverse abdominis; IO: Internal oblique; EO: External oblique

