## Objectives\*

The purpose of the study is to measure the change in pain and disability, quantify adherence and compliance before, during and after a competitive home exercise program compared to a traditional home exercise program. Additionally, to measure the change of ultrasound thickness of the lateral abdominal wall before and after a competitive home exercise program compared to a take home packet exercise program.

We hypothesize that the individuals in the gamified, competitive home exercise program will have decreased pain and disability, increased adherence and increased lateral abdominal wall activation compared to the traditional home exercise program during and after the 6-week protocol.

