**Consent and Screening: (~15-20min)**

Informed consent will be obtained for all subjects as outlined in the consent process selection for this protocol. The informed consent document will ask the participant to self-report any exclusion criteria that is listed. After obtaining informed consent, subjects will fill out a questionnaire asking previous and current health history (health history form). Demographic information will also be collected at this time, including, age, sex, height, and weight (basic demographic form) . Participants will also complete questionnaires asking about their low back pain (NumericPainRatingScale\_Question), disability (ODI2.1a\_QuestionnairesRCTLBP), credibility and exercise expectancy (CEQ\_questionnairesRCTLBP), Pain Catastrophizing questionnaire (PCS\_QuestionnairesRCTLBP) and fear avoidance beliefs (FABQ\_QuestionnairesRCTLBP). The remaining study procedures will begin immediately after eligibility determination or subjects can return at another date to complete the remainder of the study procedures. Consent, questionnaires, and surveys will be collected using REDCap.

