#### Patient Reported Outcomes (Subjective Questionnaires)

Each group will be completing the ODI, NPRS, CEQ, FABQ, PCS, Hooper and MacKinnon and Pain Catastrophizing questionnaire at baseline, after 3 weeks and after 6 weeks.

The SUS, EARS will be completed after 3 weeks and 6 weeks.

The GROC will be completed after the 6th week. All questionnaires will be completed again through REDCap at the 12, 18, and 24-month time points.

Lateral abdominal wall muscle thickness will be collected during the baseline session and during the last exercise session of the 6th week.

**6.4 Data collected during the study will include the ODI, NPRS, CEQ, FABQ, Hooper and MacKinnon and PCS questionnaire at baseline, after 3 weeks and after 6 weeks. The SUS, EARS will be completed at 3 weeks and 6 weeks. The GROC will be completed after the 6th week. All questionnaires will be**

completed again through emails notification for participants to complete through REDCap.

6.5 All questionnaires will be completed again through REDCap at the 12, 18, and 24-month time points.

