## **10.0 Inclusion and Exclusion Criteria\***

10.1 Individuals will be screened for inclusion and exclusion criteria by self-reporting while reading the consent form and prior to giving consent.

10.2 *Inclusion Criteria:* ages 18-45, biological sex of Male or Female, self-reported low back pain within the previous 6 months or greater than 3 episodes within the past 3 years

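### Section 17.1 names no baseline adjustment for ODI and NPRS; ANCOVA on the baseline scores already collected would usually narrow the intervals at almost no cost (a precision point, low severity)

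*Combined protocol and SAP*

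**What the plan says.** Section 17.1 (Data Management and Confidentiality) gives the whole questionnaire analysis in one sentence: "Mean differences, confidence intervals and effect sizes will be used to analyze questionnaires". It does not say whether the difference is between follow-up means or between changes from baseline, and it names no covariate. No other section adds a model.

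The baseline scores exist. Under Consent and Screening in section 6, "Participants will also complete questionnaires asking about their low back pain", and the list there includes the disability index. Patient Reported Outcomes repeats the schedule: "Each group will be completing the ODI, NPRS, CEQ, FABQ, PCS", together with the remaining baseline instruments, the list closing with the "Pain Catastrophizing questionnaire at baseline, after 3 weeks and after 6 weeks". Later, "All questionnaires will be completed again through REDCap at the 12, 18, and 24-month time points".

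The aims point to change compared between programs. The Study Summary has "To measure the change in pain and disability before, during and after a competitive home exercise program", and the hypothesis in section 2.0 is that the gamified group "will have decreased pain and disability, increased adherence and increased lateral abdominal wall activation compared to the traditional home exercise program". Section 12.2 plans for 34 analysable participants, 17 per group, with 80% power at alpha .05.

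**The concern.** With 17 per group, the confidence intervals that 17.1 promises will be wide. The baseline value of the same scale is often the best available predictor of the follow-up value, and section 6 already collects it. Each simple contrast uses it poorly over part of the range of r. A change score subtracts the whole baseline value, which adds noise unless r is high. A follow-up score ignores baseline, which wastes information unless r is near 0. ANCOVA estimates how much of the baseline to subtract.

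The aims make change scores the natural reading of 17.1. Against them the gain is largest when r is low. Low r is possible here, because section 10.2 admits people with "self-reported low back pain within the previous 6 months or greater than 3 episodes within the past 3 years" and sets no minimum current score, and because follow-up runs to 24 months. The documents show only that low r is possible, not that it is likely.

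**Working it through.** **Inputs from the documents.** Section 12.2: 34 analysable, 17 per group, 80% power, alpha .05, 15% attrition. The plan's total reproduces: 34 / (1 − .15) = 40, or 20 per group. The 34 cannot be rebuilt, because no effect size or SD is given. By the noncentral t, two-sided, it corresponds to a true difference of 0.99 SD.

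**Assumptions not in the documents.** Two-sided .05, equal baseline and follow-up SDs (set to 1), approximate normality, correlation r.

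**Variance of the group difference, in units of 2/n, with N = 2n:**
- follow-up score: 1, on N − 2 df
- change score: 2(1 − r), on N − 2 df
- ANCOVA: (1 − r²)(N − 3)/(N − 4), on N − 3 df. At N = 34 the last factor is 31/30 = 1.033, the price of estimating the slope.

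**Break-even correlations, N = 34.**
- Against follow-up scores: (1 − r²)(31/30) < 1 gives r² > 1/31, so r > .18.
- Against change scores: (1 + r)(31/30) < 2 gives r < 29/31 = .935. Allowing for the slightly larger t value, this is .931.
- With 20 per group the factor is 37/36, and the limits are √(1/37) = .16 and 35/37 = .95.

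**95% CI half-width = t × √(variance × 2/17)**, with t = 2.037 on 32 df and 2.040 on 31 df. Example at r = .5: follow-up or change 2.037 × √(2/17) = 0.699; ANCOVA 2.040 × √(0.775 × 2/17) = 0.616, which is 12% narrower.

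| r | Follow-up | Change | ANCOVA | ANCOVA vs change | ANCOVA vs follow-up |
|---|---|---|---|---|---|
| 0 | 0.699 | 0.988 | 0.711 | 28% narrower | 2% wider |
| .3 | 0.699 | 0.827 | 0.678 | 18% narrower | 3% narrower |
| .5 | 0.699 | 0.699 | 0.616 | 12% narrower | 12% narrower |
| .7 | 0.699 | 0.541 | 0.508 | 6% narrower | 27% narrower |
| .8 | 0.699 | 0.442 | 0.427 | 3% narrower | 39% narrower |

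At r = .9 ANCOVA is under 1% narrower than change scores.

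**Power at a true 0.99 SD** (follow-up / change / ANCOVA): 80/51/79% at r = 0, 80/66/82% at .3, 80/80/89% at .5, 80/95/97% at .7.

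**Unequal SDs.** Let k be the baseline SD divided by the follow-up SD. The change-score variance becomes 1 + k² − 2kr, and the ANCOVA variance is unchanged. At k = 0.8, change scores are better where 1.0333r² − 1.6r + 0.6067 < 0, which is r of about .66 to .88. At k = 0.7 the range is about .55 to .81. The largest loss is at r = k, where the change-score variance is 1 − r² and the ANCOVA variance is 31/30 of it: 1 − 30/31 = 3.2%.

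**Floor effects (simulation).** The assumed score runs from 0 to 10, with 40% of baseline values at zero, 17 per group and a latent effect of 0.991 SD. If the packet group does not improve, power at r = 0 is about 64.8% for follow-up scores and 63.2% for ANCOVA. If both groups also improve by 1 SD, it is about 28.3% and 25.5%, and the type I error of ANCOVA is about 4.3%. ANCOVA stays ahead of change scores in both cases.

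**The case against.** **The text leaves the model open.** Mean differences, intervals and effect sizes are summary measures, and ANCOVA also yields a mean difference with an interval. A reader might infer that the plan has chosen an unadjusted analysis. It has not: 17.1 neither plans nor excludes adjustment. That stands, and it is why the point is worded as an adjustment not named.

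**This is a preference about precision.** A reader might infer that omitting baseline biases the result. The documents do not support that, since section 6.1 randomises participants and either simple contrast is then unbiased. The size of the gain also rests on r, which the documents do not give. If r is .8 or more and the contrast is change, little is gained.

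**The .18 to .93 range is conditional.** It needs 34 analysable participants and equal SDs. With less variable baseline scores, change scores are slightly better over part of it. This stands, but that loss is at most about 3% of variance, against possible gains several times larger.

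**Floors could bite harder.** Section 5.1 gives both groups the same exercises, so both may improve. The power cost at r = 0 can then reach about 3 points rather than 1.4. This also stands. It does not restore change scores.

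**Type I error.** A reader might infer that an open contrast inflates type I error. That would require reporting whichever contrast is significant, and no passage plans this.

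**Conclusion.** The point holds as a cheap gain in precision, of low severity. Section 17.1 does not use a baseline measurement that the trial already takes. At 17 per group with equal SDs and approximate normality, ANCOVA gives a clearly narrower interval than change scores at low to moderate r, and than follow-up scores at moderate to high r. Near the ends of the range the gain is negligible. Because r is unknown and 17.1 leaves the contrast open, the case for ANCOVA is that it is never much worse than either simple contrast and often clearly better. Its absence is not an error and does not threaten validity. Which outcome and visit should be primary is a separate question and is not settled here.

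**What to change.** Add to section 17.1:

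> ODI and NPRS at each follow-up visit (3 and 6 weeks; 12, 18 and 24 months) will be compared between the randomised groups by ANCOVA, with the baseline value of that measure as covariate. We will report the adjusted between-group mean difference, its 95% CI, and the effect size standardised by the unadjusted SD. Linearity of the relation with baseline will be checked with a plot.

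The plot matters because the eligibility criteria allow low baseline scores. SUS, EARS and GROC have no baseline value in the schedule, so this does not apply to them.

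**Cost.** Wording only, with no new data or visits. The analysis gives up one residual degree of freedom (32 to 31) and takes about 3.3% variance inflation at N = 34. If r = 0, that is about 1.4 power points against follow-up scores (80.0% to 78.6% at 0.99 SD), or up to about 3 points in the strong-floor case with both groups improving. The change should be made before outcome data are examined.

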**Dynamic Ultrasound setup and exercise completion (up to ~45 min)**

The ultrasound transducer will be placed 10cm from the umbilicus over the right lateral abdominal wall with the thoracolumbar fascia visible on the ultrasound screen. The transducer will be secured with a nylon belt and foam block.

- 3 images of the PBP static position and 3 images of the PBP starting position will be obtained.
- 3 images of the TESP static position and 3 images of the TESP starting position will be obtained.
- 3 images of the FESP static position and 3 images of the FESP starting position will be obtained.

- 3 images of the dead bug static position and 3 images of the dead bug starting position will be obtained
- 3 images of the bird dog static position and 3 images of the bird dog starting position will be obtained.

A total of 30 images for the right abdominal wall will be obtained. The ultrasound transducer will then be moved to the participants left lateral abdominal wall and pictures will be repeated.

Upon the collection of 60 images, the ultrasound transducer will be taken off the participant and they will complete the PBP, TESP, FESP, dead bug and bird dog until discontinuation. The TESP and FESP will be completed bilaterally so the left and right elbow will be placed on the ground.

[figure not shown]
PBP static position and starting position:

TESP static position and starting position:

FESP static position and starting position:

Dead bug static position and starting position:

Bird dog static position and starting position:

[figure not shown]

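### Section 17.1 states an activation ratio as its one ultrasound measure, which does not measure the before-to-after change in muscle thickness set as a secondary objective

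*Combined protocol and SAP*

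**What the plan says.** The secondary objective in the Study Summary is "To measure the change of Ultrasound thickness and onset of muscle activation of the lateral abdominal wall", and it names both positions and the time frame: "during static and exercise positioning following a 6-week home exercise program". The Objectives section restates it as a comparison with the take-home packet: "to measure the change of ultrasound thickness of the lateral abdominal wall before and after a competitive home exercise program". The hypothesis in the same section is worded differently. It predicts "increased adherence and increased lateral abdominal wall activation compared to the traditional home exercise program", which concerns activation and not thickness.

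In section 6.0, under Patient Reported Outcomes, the schedule reads "Lateral abdominal wall muscle thickness will be collected during the baseline session and during the last exercise session" of week 6. The ultrasound set-up takes three images per position for each exercise, for example "3 images of the PBP static position and 3 images of the PBP starting position will be obtained", first on the right side and then on the left.

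Section 17.1 gives one treatment of these data: "An activation ratio will be used for the lateral abdominal wall measurements", with static thickness on top and starting-position thickness below. Mean differences, confidence intervals and effect sizes are stated there for the questionnaires. Section 4.0 defines the endpoint as the recruitment of 40 people and lists no ultrasound endpoint. No section states an analysis of thickness itself.

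**The concern.** A ratio of two thicknesses taken at the same visit is a different quantity from either thickness. It removes whatever the two positions share, including any growth that is proportional in both. The objective asks whether the muscle became thicker from before to after the programme, in each position and by arm. The stated measure asks how the two positions relate to each other at a visit.

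Two things are at stake. The thickness objective has no planned analysis, so any thickness result would be chosen after the data are seen, from a large set of muscles, exercises, sides and positions. A shift in the ratio could also be read as altered activation when only static thickness changed. Both problems remain if the ratio is inverted.

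**Working it through.** **Inputs from the documents.** Five exercises, two positions, three images and two sides (section 6.0, ultrasound set-up); three muscles forming the lateral abdominal wall (Background and the abbreviations list); 17 evaluable per arm (section 12.2). The documents give no thickness, standard deviation or expected gain, so the thickness values and variability below are assumptions.

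**The plan's own figures.** Images per side: 5 × 2 × 3 = 30; both sides: 60. Sample size: 34 / 0.85 = 40. Both reproduce, and neither bears on the choice of measure.

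**Step 1: same percentage gain in both positions.** Let S be static and E starting-position thickness, with R = S/E. If both rise by a proportion p:

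(1 + p)S / ((1 + p)E) = S/E

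The change in R is exactly 0 for any p. With assumed S = 3.0 mm, E = 4.5 mm and p = 10%: before, 3.0/4.5 = 0.667; after, 3.3/4.95 = 0.667.

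**Step 2: same gain in millimetres, g.** R becomes (S + g)/(E + g). With g = 0.3 mm: 3.3/4.8 = 0.688, a rise of 3.1%, while static thickness rises 10%. For other assumed pairs with the same 10% static gain:

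| S, E (mm) | R before | R after | Change in R |
|---|---|---|---|
| 3.0, 3.6 | 0.833 | 0.846 | +1.5% |
| 3.0, 4.5 | 0.667 | 0.688 | +3.1% |
| 3.0, 6.0 | 0.500 | 0.524 | +4.8% |

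The signal is diluted but not removed.

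**Step 3: attribution.** If only static thickness rises 10%, R = 3.3/4.5 = 0.733. If static thickness is unchanged and starting-position thickness falls to 4.5/1.1 = 4.09 mm, R = 3.0/4.09 = 0.733. The ratio alone cannot separate the two.

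**Step 4: illustrative power.** Simulation with 17 per arm, a two-sided t-test at 0.05 on change in log thickness or log ratio, 10% static thickening in one arm only, SD of log change 0.10 and correlation 0.5 between positions (all assumed except 17 and 0.05; the plan does not state sidedness):

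| Pattern | Static thickness | Ratio |
|---|---|---|
| Same percentage | about 77% | about 5% |
| Same mm (3.0 and 4.5 mm, +0.3 each) | about 77% | about 14% |

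The 5% is simply alpha and follows from step 1 whatever SD is assumed. The 77% and 14% depend on the assumed values.

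**Step 5: number of outcomes.** If all three muscles are measured, there are 5 × 2 sides × 2 positions × 3 muscles = 60 possible thickness outcomes and 5 × 2 × 3 = 30 ratios, in 34 to 40 people. An added thickness analysis therefore needs structure.

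**The case against.** The strongest reply is that the hypothesis predicts greater activation, not a larger muscle, and that removing resting size is what an activation ratio is for. That stands: the ratio is a sensible measure for the hypothesis and should be kept. It does not dispose of the thickness objective, which is stated separately in two places.

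A second reply is that change in thickness may mean the contrast between rest and exercise, as the Background's description of imaging suggests. The Study Summary wording allows this in part. The Objectives section does not, because it places the change before and after the programme and compares the arms.

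Third, 17.1 is brief and does not forbid reporting the components, and the thicknesses will be on file. That is correct, so the gap is in the analysis plan and not in the data. A reader might infer that any real thickening would go undetected or be reported as no change. The documents do not support that. Exact cancellation requires an equal percentage change in both positions, other patterns move the ratio to some degree, and an unchanged ratio would properly be reported as no change in activation. Nor do the documents say that proportional thickening over 6 weeks is expected.

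The same objective also names onset of activation, for which 17.1 states no analysis. That is a separate gap and is not resolved here.

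**Conclusion.** The point holds: 17.1 followed as written leaves the thickness objective without a measure that answers it. The loss is complete when both positions thicken by the same percentage, which is algebra and rests on no assumed figure. It is heavy for an equal-millimetre gain, where a 10% static gain shows as a ratio change of 1.5% to 4.8% over assumed baseline ratios of 0.83 to 0.50. The power contrast is illustrative and is not evidence about this trial.

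It would be too strong to call the ratio the wrong measure or the trial unable to study thickness: the ratio fits the activation hypothesis, and the values needed are collected. Ultrasound is a secondary objective, so the conclusions on pain and disability are unaffected. The change should be made, and made before week-6 images are compared between arms.

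**What to change.** Amend 17.1 as follows.

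- **Thickness objective.** Compare week-6 thickness (mm, mean of the three images) between arms, adjusted for the same thickness at baseline, for static and starting positions separately. Report mean differences with confidence intervals. The baseline adjustment is needed because the objective is change.
- **Structure.** Name in advance one key muscle and one key position, and state the rule for combining sides and exercises, for example averaging within participant. Label all other thickness results exploratory. The documents give no basis for choosing the key muscle and position here, so the investigators should choose them.
- **Activation hypothesis.** Keep the ratio as a separate measure, state which direction means greater activation, and always report it beside its two component thicknesses.

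The cost is wording and more secondary ultrasound results to analyse and report. Both thicknesses must already be measured to form the ratio, so no images or visits are added.
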